9.1 Archiving

It is the responsibility of the Principal Investigator to ensure all essential trial documentation and source records (e.g., signed Informed Consent Forms, Investigator Site Files, participants' hospital notes, etc.) at their site are securely retained for at least 10 years after the end of the trial. Do not destroy any documents without prior approval from the CRCTU Archivist.

10 QUALITY MANAGEMENT

10.1 Site Set-up and Initiation

All sites will be required to sign a model Clinical Trials Agreement (mNCA) prior to participation. In addition, all participating investigators will be asked to sign the necessary agreements e.g., Registration Forms and supply a current *curriculum vitae* (CV) to the Trial Office. Prior to commencing recruitment all sites will undergo a process of initiation. A light touch initiation process will be conducted for sites participating in the OCTAVE trial which utilises nearly identical procedures. For all other sites initiation meetings will be held on request. Where these are held, key members of the site research team will be invited to attend a teleconference covering aspects of the trial design, protocol procedures, collection and reporting of data and record keeping. Sites will be provided with the documentation for an Investigator Site File containing essential documentation, instructions, and other documentation required for the conduct of the trial. The Trial Office must be informed immediately of any change in the site research team.

10.2 On-site Monitoring

Monitoring will be carried out as required following a risk assessment and as documented in the OCTAVE-DUO Quality Management Plan. Additional on-site monitoring visits may be triggered for example by poor CRF return, poor data quality, low SAE reporting rates, excessive number of patient withdrawals or deviations. If a monitoring visit is required, the Trial Office will contact the site to arrange a date for the proposed visit and will provide the site with written confirmation. Investigators will allow the OCTAVE-DUO trial staff access to source documents as requested.

10.3 Central Monitoring

The Trial Office will be in regular contact with the site research team to check on progress and address any queries that they may have. Trial staff will check incoming CRF for compliance with the protocol, data consistency, missing data and timing. Sites will be sent queries through the eRDC system requesting missing data or clarification of inconsistencies or discrepancies.

Sites may be suspended from further recruitment in the event of serious and persistent non-compliance with the protocol and/or Good Clinical Practice (GCP). Any major problems identified during monitoring may be reported to the TMG and the relevant regulatory bodies. This includes reporting serious breaches of GCP and/or the trial protocol to the REC (see Section 10.5 for further details).

10.4 Audit and Inspection

The investigator will permit trial-related monitoring, audits, ethical review, and regulatory inspection(s) at their site, providing direct access to source data/documents.

Sites are requested to notify the Trial Office of any MHRA inspections.

10.5 Notification of Serious Breaches

In accordance with Regulation 29A of the Medicines for Human Use (Clinical Trials) Regulations 2004 and its amendments the sponsor of the trial is responsible for notifying the licensing authority in writing of any serious breach of:

- The conditions and principles of GCP in connection with that trial or;
- The protocol relating to that trial, within 7 days of becoming aware of that breach

For the purposes of this regulation, a “serious breach” is a breach which is likely to effect to a significant degree:

- The safety or physical or mental integrity of the subjects of the trial; or
- The scientific value of the trial

Sites are therefore requested to notify the Trial Office of a suspected trial-related serious breach of GCP and/or the trial protocol. Where the Trial Office is investigating whether or not a serious breach has occurred sites are also requested to cooperate with the Trial Office in providing sufficient information to report the breach to the MHRA where required and in undertaking any corrective and/or preventive action.

11 END OF TRIAL DEFINITION

The end of trial will be 18 months after the last participants’ last data capture. This will allow sufficient time for the completion of protocol procedures, data collection and data input, and sample analyses. The Trial Office will notify the MHRA and REC that the trial has ended and will provide them with a summary of the trial report within 12 months of the end of trial.

12 STATISTICAL CONSIDERATIONS

12.1 Definition of Outcome Measures

12.1.1 Primary Outcome Measures

The primary outcome measure is defined in Section 2.2.1.

12.1.2 Secondary Outcome Measures

Secondary outcome measures are defined in Section 2.2.2.

12.2 Analysis of Outcome Measures

Full details will be specified in a Statistical Analysis Plan (SAP) but an outline of the analysis methodologies of the primary and secondary outcome measures are provided here.

Statistical analyses will be performed using appropriate statistical software (e.g. Stata, Stata Inc, Texas, USA).

12.2.1 Primary Outcome Measures

The primary outcome assessment will be based on the immune response observed in the total combined participants recruited to both the Pfizer and Moderna vaccine arms (n=1160). Analysis will be based on the difference in immune response measured using the specified assays at baseline (pre-third vaccination booster) and then at Day 21 post-third vaccination booster using a paired T-Test analysis method.

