3 TRIAL DESIGN AND RECRUITMENT TARGETS

3.1 Trial Design

OCTAVE-DUO is a phase III, multi-centre, multi-disease, open-label, randomised trial to determine whether a re-boost vaccine strategy can induce an immune response in clinically vulnerable patients with proven inadequate response to SARS-CoV-2 vaccine. Patients with 1) solid cancer; 2) lymphoid malignancies; 3) immune-mediated rheumatic diseases; 4) end stage kidney disease; 5) chronic liver

disease; 6) gastrointestinal disease on immune suppressive therapy; 7) haematopoietic stem cell transplant; 8) primary immunodeficiency; and 9) CAR-T cell therapy who have received two doses of SARS-CoV-2 vaccine but have proven inadequate response to SARS-CoV-2 vaccine attending specialist clinics across the UK will be recruited.

Patients will be randomly allocated to receive either Pfizer or Moderna (or for a sub-set of patients Pfizer or Moderna or Novavax) SARS-CoV-2 re-boost vaccine and their immunogenic responses analysed.

If the Novavax vaccine is not available and patients have already been randomised to this arm they will be re-randomised to the Main Study randomisation (Pfizer vs. Moderna).

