3.2 Recruitment Targets

Up to 1200 participants will be recruited from the 8 different disease cohorts. The numbers recruited per cohort will vary as indicated below.

Initiation of recruitment into each cohort will be staggered with lymphoid malignancy, immune-mediated rheumatic diseases, end stage kidney, chronic liver disease, and gastrointestinal disease on immunosuppressive therapy and patients being prioritised in the initial recruitment phase of the trial.

The target recruitment for the study components (see Section 12.2.6 for power calculations) are:

- Main study - minimum of 1100 participants will contribute to the analysis
- Randomised sub-study – minimum of 300 participants will contribute to the analysis

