12.2.6 Sample Size Justification

12.2.6.1 Primary outcome sample size justification

A power calculation based on a paired T-Test was performed using Stata version 17.0 (Stata Corps, USA) to estimate the detectable effect size based on a proposed recruitment of 1100 participants (this reduction of 60 participants allows for withdrawal or loss to follow-up). It was found that with 1100 pairs using 90% power and significance (alpha) set to 5%, a very small effect size of 0.0978 would be detectable. For 800 evaluable patients with a significance (alpha) set at 5% an effect size of 0.0978 would be detectable with 79% power.

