12.2.6.2 Secondary outcome sample size justification for sub-study randomisation

There is a potential for 320 participants to be recruited to the sub-study, however, in order to allow for drop out or recruitment failures, a total number of 300 recruits has been used in the power calculation. A power calculation based on an ANOVA statistical test was carried out using Stata version 17.0 (Stata Corps, USA) to estimate the detectable effect size based on total sample size number of 300 participants, recruited into one of three treatment arms (Pfizer, Moderna or Novavax, n=100 in each arm). Using power of 80%, significance (alpha) set at 5%, an effect size of 0.1801 would be detected.

These power calculations will be revised should the recruitment numbers differ from those predicted.

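### The 1160 Pfizer and Moderna recruits, and the 1100 evaluable pairs taken from them, do not fit a 1200 ceiling once the 1:1:1 sub-study has filled its Novavax arm

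*Protocol*

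**What the plan says.** All references are to the protocol.

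- **Ceiling.** Section 3.2: "Up to 1200 participants will be recruited from the 8 different disease cohorts". Sections 3.2.1.1 to 3.2.1.9 then give targets for nine cohorts.
- **Minima.** For the main study, section 3.2 sets a "minimum of 1100 participants will contribute to the analysis". For the randomised sub-study the corresponding minimum is 300.
- **Primary analysis set.** Section 12.2.1 uses the "total combined participants recruited to both the Pfizer and Moderna vaccine arms (n=1160").
- **Primary power.** Section 12.2.6.1 is "based on a proposed recruitment of 1100 participants (this reduction of 60 participants allows for withdrawal or loss to follow-up") and finds that "with 1100 pairs using 90% power and significance (alpha) set to 5%, a very small effect size of 0.0978 would be detectable". It adds that 800 evaluable patients would give 79% power at the same effect size.
- **Sub-study.** Section 6.1.2 randomises lymphoid patients 1:1:1. Section 12.2.6.2 allows for up to 320 but powers on 300, "recruited into one of three treatment arms (Pfizer, Moderna or Novavax, n=100 in each arm").
- **Overlap.** The footnote to the Trial Design diagram brings the sub-study's Pfizer and Moderna patients into the main comparison. It also lets lymphoid patients enter the main study only.
- **Novavax supply.** Under section 3.1, if Novavax is unavailable, patients already allocated to it "they will be re-randomised to the Main Study randomisation (Pfizer vs. Moderna").

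**The concern.** Every Novavax patient counts towards the 1200 but not towards the primary analysis. A Pfizer and Moderna total of 1160 leaves 40 places for Novavax, while section 12.2.6.2 plans 100. So the total ceiling, the primary recruitment figure, the evaluable figure with its loss allowance and the sub-study size cannot all hold together.

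At stake is whether the sample size quoted for the primary analysis is one that the design can deliver, and whether the stated 90% power therefore describes this trial.

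**Working it through.** **1. Reproduce the protocol's power figures.** Paired t-test, noncentral t with n − 1 degrees of freedom and noncentrality d√n, alpha 5%. The protocol does not state sidedness.

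- Two-sided, n = 1100, d = 0.0978: power 89.99%. Solving for 90% power gives d = 0.0978. The normal approximation (1.960 + 1.282)/√1100 gives 0.0977.
- Two-sided, n = 800, d = 0.0978: power 78.9%, against the stated 79%.
- One-sided, n = 1100: power would be 94.5% and the detectable effect 0.0883, so the calculation was two-sided.

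Both stated figures reproduce.

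**2. Add the cohort targets** (sections 3.2.1.1 to 3.2.1.9).

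80 + 320 + 160 + 160 + 80 + 80 + 80 + 160 + 80 = 1200.

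The targets use the whole ceiling, with nothing spare.

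**3. Count Pfizer and Moderna recruits.** Recruits = 1200 − (sub-study size)/3.

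- Sub-study 300: 1200 − 100 = 1100.
- Sub-study 320: 1200 − 106.7 = 1093.

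The stated figure is 1160. Working backwards, 1200 − 1160 = 40 on Novavax, which under 1:1:1 is a sub-study of 120. Keeping 1160 together with the planned Novavax arm needs 1160 + 100 = 1260 to 1160 + 107 = 1267 recruits.

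**4. Apply the protocol's loss allowance.** The rate is 60/1160 = 5.2%, so evaluable = recruits × 1100/1160. Taking off a flat 60 is shown as an alternative.

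| Sub-study size | Pfizer + Moderna recruits | Loss applied | Evaluable pairs | Power at 0.0978 | Effect at 90% power |
|---|---|---|---|---|---|
| 300 | 1100 | none | 1100 | 90.0% | 0.0978 |
| 300 | 1100 | 5.2% | 1043 | 88.4% | 0.1005 |
| 300 | 1100 | 60 | 1040 | 88.3% | 0.1006 |
| 320 | 1093 | none | 1093 | 89.8% | 0.0981 |
| 320 | 1093 | 5.2% | 1037 | 88.2% | 0.1008 |
| 320 | 1093 | 60 | 1033 | 88.1% | 0.1009 |

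**5. Check the two minima in section 3.2 against the ceiling.** Of 300 analysed sub-study patients, 200 are on Pfizer or Moderna and already count in the main study. Distinct patients needed = 1100 + 100 = 1200. That is the entire ceiling, so both minima hold only if nobody is lost. With 320 in the sub-study, 1093 is below 1100 even with no loss.

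**The case against.** The best defence has four parts.

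- **The power statement is conditional and correct.** It says what 1100 pairs would detect, and it reproduces. This stands. A reader might infer that the power calculation is wrong; the document does not support that. Only the head-count feeding it is at fault.
- **A shortfall is already covered.** Section 12.2.6.1 reports power at 800 evaluable, a worse case than 1037 to 1043, and section 12.2.6.2 promises revision if recruitment differs from prediction. The first shows that little depends on the gap. The second does not cure it, because the conflict exists at the predicted numbers.
- **The main study can gain patients.** Lymphoid patients may join the main study only, and Novavax allocations can be re-randomised. Both raise the Pfizer and Moderna count, but each lowers the Novavax count. Reaching 1160 gives up the sub-study minimum of 300.
- **1100 evaluable is not strictly impossible.** With 300 in the sub-study and no losses it is met exactly. This also stands. The conflict arises once any loss occurs, and the protocol itself allows for 60.

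A reader might also infer that Novavax is really planned at 40, with a serious loss of sub-study power. Nothing in the protocol plans that: section 6.1.2 fixes 1:1:1 and section 12.2.6.2 states 100 per arm. The plainer reading is that 1160 does not belong with the other figures.

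**Conclusion.** The concern holds as an inconsistency in stated figures. On the protocol's own ceiling, allocation ratio and sub-study size, 1093 to 1100 patients are recruited to Pfizer or Moderna, which is 60 to 67 fewer than stated. At its own loss rate about 1037 to 1043 pairs are evaluable, which is 57 to 63 fewer than stated.

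The effect on the primary analysis is small: power at 0.0978 falls from 90% to about 88%, or the effect detectable with 90% power rises from 0.0978 to about 0.1005 to 0.1008. The protocol already calls 0.0978 very small, so the primary conclusion is not threatened.

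This rests on three assumptions: recruitment reaches but does not exceed 1200, the sub-study fills to 300 to 320 with Novavax available, and losses in the Pfizer and Moderna arms run at 60 in 1160. The protocol does not explain where 1160 comes from, so it cannot be said which of the conflicting figures was intended.

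**What to change.** Reconcile sections 3.2, 12.2.1, 12.2.6.1 and 12.2.6.2 so that one set of numbers runs through all four.

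If the 1200 ceiling and the sub-study stand:

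- Section 12.2.1: replace 1160 with 1093 (sub-study of 320) or 1100 (sub-study of 300).
- Sections 3.2 and 12.2.6.1: replace 1100 evaluable with about 1040, and recast the 60-patient reduction from the corrected recruitment figure.
- Section 12.2.6.1: state 88% power at 0.0978, or a detectable effect of about 0.1005 to 0.1008 at 90% power. The 800-patient statement can stay as it is.
- Section 12.2.6.2: show the Novavax number being subtracted from the total, so that the link to section 12.2.1 is visible.

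If 1160 was intended, state its basis and change whichever other figure gives way: a ceiling of about 1260 to 1267, or a smaller sub-study with its power restated.

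The first route changes wording only, needs no extra patients, and costs about 2 points of stated power.

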12.2.2 Secondary Outcome Measures

Assay data from the subset of lymphoid malignancies, randomised into one of either Pfizer, Moderna or Novavax vaccine arms, will be analysed using repeated measure analysis of variance (ANOVA) with a Tukey's post-hoc test to detect differences in groups if any significant differences are detected.

Analysis of the IgG (pseudo) neutralisation assay data will be analysed using repeated measure ANOVA with a Tukey's post-hoc test to detect differences between groups if any significant differences are detected.

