1.1.1 OCTAVE-DUO Trial Hypotheses

The specific hypotheses are:

- Patients with no detectable SARS-CoV-2 specific immunoglobulin (Ig) antibodies after two doses of vaccines have failed to prime SARS-CoV-2 humoral responses and will not respond to an additional booster vaccine, whereas patients with low but detectable SARS-CoV-2 Ig responses have successfully primed responses and are likely to benefit from an additional re-boost vaccination.
- The absence/presence of SARS-CoV-2 specific T-cells in patients with no/low SARS-CoV-2 specific Ig antibodies after two vaccines may identify patients who will respond to re-boost strategies.
- Patients with unified clinical phenotypes (e.g., same underlying primary disease, or common immune suppressive drugs in different disease states) will respond similarly to re-boost vaccinations.

The OCTAVE DUO trial represents the most extensive study of sub-optimal vaccine responses in chronic disease.

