6.1.2 Sub-study Randomisation

For the sub-study randomised comparison, patients will be randomised in a 1:1:1 ratio using a minimisation program with the following stratification variables:

- Lymphoid malignancies sub-cohort diseases:
 - o Aggressive B-NHL
 - o CLL
 - o Hodgkin Lymphoma

- o Indolent B NHL
- o Myeloma
- Prior SARS-CoV-2 vaccine type: AstraZeneca; Pfizer; Moderna; Other
- SARS-CoV-2 vaccine response: antibody non-responders or antibody low-responders as defined above.

Patients will be randomised to receive:

- Arm 1: Pfizer SARS-CoV-2 Vaccine; or
- Arm 2: Moderna SARS-CoV-2 Vaccine; or
- Arm 3: Novavax SARS-CoV-2 Vaccine.

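### The ANOVA named for the three-vaccine sub-study carries none of the minimisation factors, so it is conservative, and weaker than an adjusted analysis, to the extent that those factors predict response

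*Protocol*

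**What the plan says.** Protocol section 6.1.2 sets the allocation: "For the sub-study randomised comparison, patients will be randomised in a 1:1:1 ratio using a minimisation program with the following stratification variables". There are three variables: "Lymphoid malignancies sub-cohort diseases" (five listed), "Prior SARS-CoV-2 vaccine type: AstraZeneca; Pfizer; Moderna; Other" (four levels) and "SARS-CoV-2 vaccine response: antibody non-responders or antibody low-responders as defined above" (two levels).

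Section 12.2.2 sets the analysis of that comparison. Assay data of these patients, "randomised into one of either Pfizer, Moderna or Novavax vaccine arms, will be analysed using repeated measure analysis of variance (ANOVA) with a Tukey's post-hoc" procedure. No factor or covariate is mentioned. The same method is named for the neutralisation assay, and section 12.2.4 carries it over to the exploratory analyses where appropriate.

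Section 12.2.6.2 powers the sub-study with an ANOVA on 300 patients, 100 per arm: "Using power of 80%, significance (alpha) set at 5%, an effect size of 0.1801 would be detected".

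Section 1.1.1 expects one of the three factors to be prognostic. Patients without detectable antibody after two doses "will not respond to an additional booster vaccine, whereas patients with low but detectable SARS-CoV-2 Ig responses have successfully primed responses"; the latter group is expected to benefit.

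Section 12.2 calls all this an outline and leaves full detail to a SAP, which is not at hand.

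**The concern.** Minimisation makes the arms alike on the three factors, so differences between factor levels contribute almost nothing to the differences between arm means. An ANOVA with vaccine group alone still counts those differences as error. Its F and Tukey reference distributions assume more chance variation between arms than the design allows. The p-values are then too large and the intervals too wide.

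The risk is a missed difference between vaccines, not a false claim of one. That still matters here, because a non-significant three-vaccine comparison is easily read as showing that the vaccines are alike.

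**Working it through.** **Inputs from the protocol.** N = 300, three arms of 100, alpha 5%, power 80%, effect size f = 0.1801 (section 12.2.6.2); factors with 5, 4 and 2 levels (section 6.1.2); sub-type targets of 40, 80, 40, 80 and 80 (section 3.2.1.2).

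**Assumed, because the protocol does not give it.** R², the share of variance of the analysed value that the factors explain, from 0 to 0.5. For the simulation: prior-vaccine frequencies 50/45/3/2%, non-responders 40%, half of the explained variance due to responder status and a quarter to each other factor, and minimisation that picks the best-balanced arm with probability 0.8 and otherwise any arm at random.

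**1. The plan's own figure.** One-way ANOVA, k = 3, N = 300, noncentrality N·f² = 300 × 0.1801² = 9.73. Noncentral-F power is 79.99%, and solving for 80% gives f = 0.1801. The figure reproduces as an ANOVA without covariates, so the power calculation and section 12.2.2 describe the same unadjusted test.

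**2. Which R² counts.** With two time points, the group-by-time test of a repeated-measures ANOVA equals a one-way ANOVA on the change from baseline to day 21. Stable differences between patients drop out. R² therefore means the share of the variance of the *change* that the factors explain.

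**3. Size of the unadjusted test.** With the factors balanced, the between-arm statistic varies as (1 − R²) times its nominal distribution. Hence

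size ≈ P(χ²₂ > 5.99/(1 − R²)) = exp(−2.996/(1 − R²)).

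At R² = 0.2 this is exp(−3.745) = 2.4%.

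**4. Power.** Adjustment removes the factor variance from the error, so f becomes f/√(1 − R²) and the noncentrality becomes 9.73/(1 − R²). At R² = 0.2 that is 12.16, and power is 88.4%. The unadjusted test has the same noncentrality but must pass the raised threshold 5.99/(1 − R²), which gives 82.0%.

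**5. Simulation check.** 4,000 null and 1,500 alternative trials per row. The Monte Carlo standard error is about √(0.05 × 0.95/4000) = 0.3 points for size and √(0.8 × 0.2/1500) = 1.0 point for power.

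| R² (assumed) | Size, formula | Size, simulated | Unadjusted power at f = 0.1801, simulated | Adjusted power, simulated |
|---|---|---|---|---|
| 0 | 5.0% | 5.0% | 80.5% | 80.6% |
| 0.05 | 4.3% | 4.0% | 80.8% | 82.7% |
| 0.1 | 3.6% | 3.4% | 81.1% | 84.1% |
| 0.2 | 2.4% | 2.4% | 81.7% | 88.1% |
| 0.3 | 1.4% | 1.4% | 82.5% | 91.6% |
| 0.5 | 0.25% | 0.2% | 84.9% | 98.5% |

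The size columns refer to the unadjusted test. The adjusted test had size 5.0% in every row. With equal arms formed without regard to the factors, the unadjusted size at R² = 0.3 was 5.3%, nominal within error. So the cause is the pairing of minimised allocation with an unadjusted test.

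**6. What R² responder status alone could give.** For a share p of non-responders and a difference in mean change of d within-group SDs, R² = p(1 − p)d²/(1 + p(1 − p)d²). With p assumed between 0.3 and 0.5:

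- d = 0.5: R² 0.05–0.06, size 4.3–4.2%
- d = 1: R² 0.17–0.20, size 2.7–2.4%
- d = 1.5: R² 0.32–0.36, size 1.2–0.9%

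**The case against.** **The covariate list belongs in the SAP.** Section 12.2 is declared an outline, it does not call the ANOVA unadjusted, and the unseen SAP may add the factors. This stands against saying that the trial ignores them. It does not remove the point: the protocol names a test and a post-hoc procedure, and powers that test without covariates. The method as stated does not match the protocol's own allocation.

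**The loss rests on an R² that nobody gives.** This stands. A reader might infer that the true error rate is well below 5%. The documents do not support that as a fact. At R² of 0.05–0.1 the size is 3.4–4.0%; it reaches half of nominal only at about 0.2. Section 1.1.1 makes a sizeable R² plausible for responder status and antibody response, but it is a hypothesis and gives no figure, for T cells and neutralisation least of all.

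**The planned power is kept.** This also stands. A reader might infer that the sub-study is underpowered. It is not on this account: unadjusted power at f = 0.1801 is 80.5–84.9%, and the loss exists only relative to an adjusted analysis.

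**The scope is narrow.** A reader might extend the point to every comparison in the trial. Section 12.2.2 names no Pfizer-versus-Moderna test for the main study, and it does not say that the groups compared for neutralisation are vaccine arms. The primary paired t-test is within-patient and pools the arms, so allocation does not enter it.

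**Conclusion.** The point holds as a mismatch between design and stated analysis in the three-vaccine sub-study. If the minimisation factors predict the change from baseline to day 21, the test named in section 12.2.2 is conservative and gives away power that the data could supply. At f = 0.1801 the power forgone is about 3 points at R² = 0.1 (84.1 − 81.1), 6 at 0.2 (88.1 − 81.7), 9 at 0.3 (91.6 − 82.5) and 14 at 0.5 (98.5 − 84.9). At R² = 0.2, adjusting is worth about as much as 300/(1 − 0.2) = 375 patients analysed without adjustment.

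The direction does not depend on the assumptions, but the size does: on R² above all, and less on the factor frequencies and the random element of the minimisation. If R² is near zero, nothing is lost. No false-positive vaccine difference arises from this, the stated power is met, and the primary analysis is untouched. It is a worthwhile and cheap improvement, not a flaw that endangers the trial's main conclusion.

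**What to change.** In section 12.2.2, state that between-vaccine comparisons in the sub-study use a linear model (ANCOVA) of the day-21 value on vaccine arm, baseline value and the three minimisation factors, with Tukey-adjusted pairwise contrasts taken from that model. Merge sparse prior-vaccine levels, such as Moderna and Other, if few patients fall in them.

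If the group-by-time test is kept, model the change score with the factors, or add factor-by-time terms to the repeated-measures model. Factor main effects alone would not repair that test, because they do not touch the variance of the change.

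Apply the same to neutralisation wherever the groups compared are vaccine arms. For any Pfizer-versus-Moderna comparison in the main study, use the factors of section 6.1.1, where disease cohort takes the place of lymphoid sub-type.

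The cost is a short change to section 12.2.2, matching text in the SAP, and a few degrees of freedom: at most 4 + 3 + 1 = 8 for the sub-study factors plus 1 for baseline, out of 300 patients. No new data are needed, since the factors are recorded at randomisation (sections 6.1 and 9).

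### The sub-study's repeated-measures ANOVA does not name the tested term and is not tied to the one-way ANOVA used for power, so 80% is not assured; a baseline-adjusted ANCOVA would secure it.

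*Protocol*

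**What the plan says.** Section 12.2.2 of the protocol fixes the sub-study method. Assay data from the Pfizer, Moderna and Novavax arms "will be analysed using repeated measure analysis of variance (ANOVA"), followed by Tukey's post-hoc test on groups. The post-hoc test is to run "to detect differences in groups if any significant differences are detected". The IgG (pseudo)neutralisation data get the same model and post-hoc test, and section 12.2.4 extends these methods to the exploratory analyses where appropriate.

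The sample size is in section 12.2.6.2: "A power calculation based on an ANOVA statistical test was carried out using Stata version 17.0". Patients are "recruited into one of three treatment arms (Pfizer, Moderna or Novavax, n=100 in each arm"), and "Using power of 80%, significance (alpha) set at 5%, an effect size of 0.1801 would be detected". No time factor, correlation, response variable or SD unit is given.

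Three other sections bear on the point. Section 2.2.1 gives two measurement times, before the re-boost and day 21. Section 2.2.2 describes the sub-study outcome as a change in immunogenicity. Section 6.1.2 says "patients will be randomised in a 1:1:1 ratio using a minimisation program with the following stratification variables", and lists lymphoid sub-type, prior vaccine type and antibody response class.

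**The concern.** A repeated-measures ANOVA with three arms and two time points contains three effects: group, time and group-by-time. Only the group and group-by-time effects concern differences between vaccines, and they answer different questions.

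- **Group main effect.** This is the literal reading of a Tukey test on groups. It compares arm means averaged over the baseline and day-21 samples. Randomised arms are equal in expectation before vaccination, so averaging halves any vaccine difference present at day 21.
- **Group-by-time.** This fits the change outcome in section 2.2.2. It is valid, and with two time points it is the same test as a one-way ANOVA on each patient's change. It is less efficient than baseline adjustment when baseline and day-21 values correlate weakly.

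The trigger for the post-hoc test is also loose. As worded, a significant time effect could satisfy it, and a rise over time is what the primary objective looks for in every arm.

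At stake is the sub-study's stated formal comparison involving Novavax. The protocol attaches 80% power to it without saying which analysis, or which SD units, the 80% belongs to.

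**Working it through.** **Inputs.** From section 12.2.6.2: N = 300, three arms of 100, alpha 5%, power 80%, effect size 0.1801. From section 2.2.1: two time points. Not in the protocol, so assumed and varied: the baseline/day-21 correlation ρ and the ratio s of baseline SD to day-21 SD.

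**Step 1: reproduce the stated figure.** For a one-way ANOVA with one value per patient, the omnibus F test has 2 and 297 degrees of freedom and noncentrality N·f² = 300 × 0.1801² = 9.73. Power is 79.99%. Solving for 80% gives f = 0.1801. The stated figure is correct for that test.

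**Step 2: translate it to the candidate analyses.** Assume f = 0.1801 is in day-21 SD units and there is no arm difference at baseline. Set the day-21 SD to 1. The effective effect sizes are:

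- group main effect: (f/2) / √[(1 + s² + 2ρs)/4] = f / √(1 + s² + 2ρs)
- group-by-time (change): f / √(1 + s² − 2ρs)
- ANCOVA (day 21 adjusted for baseline): f / √(1 − ρ²)

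Example with s = 1, ρ = 0.3: 0.1801/√2.6 = 0.1117; 0.1801/√1.4 = 0.1522; 0.1801/√0.91 = 0.1888. Entered in the noncentral F with N = 300, these give 39%, 65% and 84%.

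**Step 3: power over a range.**

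| Baseline SD / day-21 SD | ρ | Group main effect | Group-by-time | ANCOVA |
|---|---|---|---|---|
| 1 | 0.1 | 45% | 53% | 80% |
| 1 | 0.3 | 39% | 65% | 84% |
| 1 | 0.5 | 34% | 80% | 90% |
| 0.5 | 0.1 | 66% | 74% | 80% |
| 0.5 | 0.3 | 60% | 82% | 84% |
| 0.5 | 0.5 | 55% | 90% | 90% |

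Over the wider grid (ρ from 0 to 0.7, s from 0.25 to 1) the main effect has 31–77%, group-by-time 49–97%, and ANCOVA 80–98%. Simulation with equal SDs at ρ = 0.3, 0.5 and 0.7 agreed with the formulas for the first two: 38/34/31% and 64/80/96%.

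**Step 4: why ANCOVA is never the weaker choice.** The variance term for change exceeds that for ANCOVA by (1 + s² − 2ρs) − (1 − ρ²) = (s − ρ)², and the term for the main effect exceeds it by (s + ρ)². Neither can be negative. This ignores the few degrees of freedom spent on covariates, which matter little at N = 300.

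**Step 5: the other choice of units.** If f = 0.1801 is in SD-of-change units, the one-way ANOVA that was powered is the group-by-time test, and it has 80% at any correlation. By Step 4, ANCOVA then has at least that.

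**The case against.** The strongest reply is that nothing is shown to be underpowered. Section 2.2.2 defines the outcome as a change, which points to group-by-time and averages nothing. The primary calculation in section 12.2.6.1 uses a paired t-test, so its effect size is naturally in SD-of-difference units. Reading 0.1801 in the same way makes the powered and planned tests identical. This stands. A reader might infer from section 12.2.2 that the baseline sample is averaged into the vaccine contrast and that the 80% is lost. The protocol supports neither as fact, because it fixes neither the tested term nor the units.

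It is also tempting to argue that the correlation must be weak because entry requires antibody below 400 AU/mL, with a class below 0.8. That is plausible but not established. The entry result may come from an earlier sample or another assay, the analysed baseline is a separate research sample, and T-cell responses are not restricted by entry. Restricting baseline would also shrink its SD, which favours group-by-time. No power shortfall can be claimed for neutralisation, since the protocol states no power for it.

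Two further points have force. Tukey's procedure controls the family-wise error of the pairwise comparisons without a preliminary test, so the loose trigger has limited effect. Leaving the minimisation factors out generally makes standard errors conservative, and covariates may properly be set in the SAP.

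Deferral to the SAP (section 12.2) is not a full answer. Section 12.2.2 already names the model, the post-hoc test and its trigger. A SAP that follows it inherits the ambiguity, and one that uses ANCOVA departs from it.

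**Conclusion.** The concern holds in limited form. The 0.1801 is right for a one-way ANOVA, but the protocol does not link it to a named term or response in the planned repeated-measures ANOVA. Whether 80% is reached depends on choices that the protocol leaves open:

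- **Day-21 units, group main effect:** below 80% in every scenario tried (31–77%).
- **Day-21 units, group-by-time:** with equal SDs, 80% at a correlation of 0.5 and more above it, but less below; 49–97% over the whole range.
- **Change-score units, group-by-time:** 80% as stated.
- **ANCOVA:** about 80% or more under either choice of units.

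The reproduction of 0.1801 is firm. The power ranges rest on assumed correlations and SD ratios, N = 300, and no arm difference at baseline. Group-by-time would be a valid analysis, so the case for ANCOVA is efficiency and certainty about the stated power, not correction of a bias.

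**What to change.** In section 12.2.2, replace the repeated-measures ANOVA for the sub-study by ANCOVA of the day-21 response on a log scale. The model terms are vaccine, baseline response on the same scale, and the three minimisation factors of section 6.1.2. Apply Tukey-adjusted pairwise comparisons to the vaccine term only, triggered by that term and not by a time effect.

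Use the same model form for the randomised vaccine comparison of neutralisation, with the minimisation factors of the relevant randomisation (section 6.1.1 or 6.1.2).

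In section 12.2.6.2, state the response variable and SD units to which 0.1801 and 80% refer. If these are day-21 units, add that 80% is approximately a lower bound under ANCOVA.

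The cost is protocol wording and matching SAP text. Both samples and all three factors are already collected, no patients are added, and under the assumptions above power stays the same or rises.
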